Eligibility determination, informed consent, demographics, medical and ophthalmic history (including a detailed history of the management of their uveitis over the previous 52 weeks), vital signs, clinical laboratory testing, ophthalmic examinations (includes BCVA, IOP, dilated ophthalmoscopy, and anterior, posterior and intermediate slit lamp examination), subjective ocular tolerability and discomfort assessment, concomitant medications, and pregnancy testing as appropriate.

Treatment Day (Day 1):

Eligibility confirmation including meeting the entry criteria for anterior chamber cells, vitreous haze, IOP, and visual acuity on Study Day 1, and then randomization to either intravitreal Yutiq 0.05 mg or sham injection. Following determination of study eye, subjects will receive either Yutiq 0.05 mg or the sham injection. Assessments on that day will include vital signs, ophthalmic examinations, spectral-domain – optical coherence tomography (SD-OCT), subjective ocular tolerability and discomfort assessment, pregnancy test if appropriate, concomitant medications, and adverse events (AEs).

Follow-up Visits:

Following injection on Study Day 1, subjects who were treated with Yutiq 0.05 mg will return for study visits on Days 7, 28, and at Months 2, 3, 6, and 12. Evaluations on these days will include: review of concomitant medications, vital signs, ophthalmic examinations, IOP, SD-OCT, subjective ocular tolerability and discomfort assessment, and AEs. All subjects treated with Yutiq 0.05 mg in the study will be followed for 52 weeks. In early May 2022, those subjects who had been treated with sham injection were discontinued from the study. Sham-treated subjects subsequently had their End of Study (EOS) evaluation.

Masking: Study subjects will receive either Yutiq 0.05 mg or a sham injection. Subjects and study staff conducting clinical study assessments, except for the clinician performing the injection procedure, will be masked to randomized treatment assignment.

Concomitant Medications:

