11.4.4 Efficacy Analyses

Efficacy analyses will be performed on both the ITT and PP populations at 24 and 52 weeks. The primary efficacy analysis will be performed on the ITT population at 24 weeks and will be the proportion of subjects who have a recurrence of uveitis. The exact 95% CI for the proportion will be derived. Hypothesis testing using the exact binomial test will be conducted to test the

difference between the proportion of subjects with a recurrence using a 2-sided alpha = 0.05. The primary efficacy analysis will be conducted after all subjects in the study have completed at least 24 weeks of study or have discontinued.

In addition to recurrence based on vitreous haze increase or BCVA loss as defined above, recurrence will also be imputed in the following circumstances:

- A subject who has not previously experienced a recurrence and does not complete the required eye examinations at Week 24 (or at Week 52 for the Week 52 analyses) for any reason will be considered as having a recurrence.
- A subject who has not previously experienced a recurrence and takes a prohibited systemic concomitant medication or a prohibited local concomitant medication in the study eye at any time during the study prior to Week 24 (or prior to Week 52 for the Week 52 analyses) will be considered as having a recurrence.

Systemic medications or topical steroids administered as part of gradual dose reduction (tapering) will not be considered prohibited medications. Topical steroids, including those administered as part of short-term standard treatment following an ocular surgical procedure, will also not be considered prohibited medications.

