1.2. Study Design

The protocol was originally planned to be a 52-week, prospective, randomized, masked (subject and outcome assessor), controlled, safety and efficacy study of intravitreal Yutiq 0.05 mg compared to sham injection with a primary efficacy and safety readout at 24 weeks. A total of approximately 60 subjects (30 subjects in the Yutiq 0.05 mg group and 30 in the sham treatment group) were to be enrolled at approximately 40 sites in the US. One eye in each subject will be designated as the study eye.

The Sponsor decided to stop enrollment in early May 2022 for reasons other than safety or efficacy, following FDA advice received on January 24, 2022. Subjects who were randomized to Yutiq 0.05 mg will continue to be monitored on a modified-protocol schedule through Month 12 (or ET) and evaluated for efficacy and safety. Those subjects who had been treated with sham injection were discontinued from the study and subsequently had their End of Study (EOS) evaluation.

[figure not shown]
Subjects will receive either Yutiq 0.05 mg or a sham injection on Day 1 of the study on the study eye and will be assessed over the following 52 weeks according to the schedule of study procedures and assessment.

Yutiq 0.05 mg is a non-erodible intravitreal implant in a drug delivery system that contains 0.05 mg of FA and is designed to release FA at a rate of 0.25 µg/day into the vitreous humor for at least 6 months. Yutiq 0.05 mg is preloaded into a single-dose applicator to facilitate injection of the implant directly into the vitreous.

To ensure the health of both eyes, observations of both the study eye and non-study (fellow) eye

should be made at all visits as described in the schedule of study procedures and assessments. Ocular data will be collected for both eyes at all visits except for the SD-OCT assessments.

Figure 1. Study Design Schema

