3.1. Intent-to-Treat Analysis Set

The Intent-to-Treat (ITT) analysis set will include all subjects who are randomized. Subject will be classified according to the assigned treatment. The ITT set will be used for analysis of efficacy, unless otherwise specified.

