4.2. Primary Efficacy Endpoint Analysis

4.2.1. Definition of Endpoint

The primary efficacy endpoint is the proportion of subjects who have a recurrence of uveitis in the study eye within 24 weeks (6 months) after receiving study treatment. Recurrence is defined as:

- An increase in the vitreous haze of ≥ 2 steps compared to baseline at the Week 24 visit, or any visit time point prior to the Week 24 visit after the Study Day 7 visit

Or

- A deterioration in visual acuity of at least 15 letters BCVA compared to baseline at the Week 24 visit, or any visit time point prior to the Week 24 visit after the Study Day 7 visit.

Any criterion used to define recurrence must be attributable only to noninfectious uveitis. To prevent post-procedural inflammatory reactions from being reported as uveitis recurrences, assessments for recurrence of uveitis begin after the Study Day 7 visit.

The study protocol stated to impute subjects who don't complete Week 24 eye examinations and subjects who take prohibited medications as having a recurrence. Consider the fact that the study was terminated early, no imputation will be implemented. Summary of the primary efficacy endpoint will be based only on the observed data from the subjects who reached Week 24.

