4.4.1. Extent of Exposure

Subjects will receive either intravitreal Yutiq 0.05 mg or sham injection in the designated study eye on Day 1 and will be followed for 52 weeks after treatment for change in IOP and for endophthalmitis. The number and percentage of subjects who remain on the study will be summarized for each visit by treatment group. The number of subjects in each treatment group will be presented based on the actual treatment they have received.

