4.8. Changes to Protocol-planned Analyses

There are modifications from the clinical study protocol amendment (protocol version 3.0, 20 July 2022) that impact statistical analysis.

- Hypothesis testing using the exact binomial test will not be conducted to test the difference between the proportion of subjects with a recurrence using a 2-sided alpha = 0.05 due to insufficient sample size. Instead, the number and proportion of subjects who experience the uveitis recurrence will be summarized by treatment group.
- Analysis populations are defined to include subjects who are randomized for the study.

5. Sample Size Determination

A total of approximately 60 subjects will be enrolled in the study and receive either Yutiq 0.05 mg or a sham injection. The Sponsor decided to stop enrollment for reasons other than safety or efficacy, following FDA advice received on January 24, 2022. In early May 2022, subject enrollment into the study has been stopped; therefore, the sample size will represent the number of subjects enrolled at the time of the Sponsors decision to stop enrollment.

6. Supporting Documentation

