6.2. Appendix 2: Supporting Study Information

6.2.1. Disposition of Subjects

A summary table will be prepared indicating the number and percentage of subjects in each treatment group who are included in each analysis population. Within the ITT population, the number and percentage of subjects who did/did not complete the study will be presented. Screen failures, including reasons for failing to satisfy eligibility criteria will also be summarized. In addition, randomization stratification and subgroups will be summarized.

Subjects who discontinue any time during the study will be summarized by reason for termination. Duration of study participation and insert duration will also be tabulated.

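### The Week 24 recurrence proportion leaves out recurrences already observed in subjects who stopped earlier, and no planned table separates them or uses their follow-up

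*SAP*

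**What the plan says.** **Event window and denominator.** SAP 4.2.1 defines recurrence as a haze increase of at least 2 steps or a loss of at least 15 letters from baseline. It may occur at Week 24 or at an earlier visit after Day 7, and must be attributable to non-infectious uveitis. The section then drops the protocol's imputation because of early termination and adds: "Summary of the primary efficacy endpoint will be based only on the observed data from the subjects who reached Week 24". SAP 4.1.3 takes Week 24 from the nominal Month 6 visit and does no re-mapping, so an end-of-study (EOS) visit does not become a Month 6 visit.

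**Protocol rule.** Protocol 11.4.4 imputed a recurrence for "A subject who has not previously experienced a recurrence and does not complete the required eye examinations at Week 24". A recurrence seen before the missed visit was therefore observed, not imputed.

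**The stop.** SAP 1.2: "Those subjects who had been treated with sham injection were discontinued from the study and subsequently had their End of Study (EOS) evaluation". Yutiq subjects continue to Month 12 or early termination (ET).

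**Analysis set and listed changes.** SAP 3.1: "The ITT set will be used for analysis of efficacy, unless otherwise specified". SAP 4.8 lists the dropped hypothesis test and one other change: "Analysis populations are defined to include subjects who are randomized for the study". It does not list the Week 24 denominator.

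**What else is tabulated.** SAP 4.2.2 gives the haze and BCVA components at each scheduled visit. SAP 4.3.1.3 counts recurrences, and SAP 4.3.2 places secondary analyses in ITT on observed data. On numbers, SAP 4.4.1 says "The number and percentage of subjects who remain on the study will be summarized for each visit by treatment group", and SAP 6.2.1 says "Within the ITT population, the number and percentage of subjects who did/did not complete the study will be presented". SAP 4.2.3 plans no sensitivity analysis. Time to recurrence (Protocol 10.2) is not in the SAP's endpoint list.

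**The concern.** The event window and the denominator do not match. A sham subject with a documented Month 2 recurrence who was discontinued in May 2022 contributes nothing to the primary row, although the event is observed data. Dropping imputation does not require this, because the protocol never imputed such a subject.

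The sponsor's stop acts on one arm. The primary row could show few sham recurrences, or have no sham subjects at all, although recurrences had been documented. Stopped subjects' follow-up also carries information about 24-week risk, which no planned estimate uses. In the Yutiq arm the rule removes anyone who leaves before Month 6 for another reason, and that loss could be related to outcome.

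**Working it through.** **The only stated design figure** is about 60 subjects, 30 per arm (SAP 1.2). No recurrence rates or power are given, so it cannot be reproduced; the point does not depend on it.

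**Step 1: the rule on assumed counts.** Take 10 sham subjects. Five reach Week 24, two of them with a recurrence; five stop earlier, k of them with a recurrence already seen. The SAP row is 2/5 = 40% (Clopper-Pearson 95% CI 5% to 85%) for every k from 0 to 5. It does not respond to k.

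**Step 2: calendar.** Reading early May as 1 to 7 May 2022, a stopped sham subject had completed 168 days only if treated by 14 to 20 November 2021. Protocol Table 5-1 allows ±28 days at Month 6. For a stop on 7 May, the latest treatment date is then 4 December 2021 if Month 6 means Day 182 (182 − 28 = 154 days), or 18 December if it means Day 168 (140 days). Enrolment dates are not given.

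**Step 3: illustration.** Assumptions, none from the documents: 15 sham subjects; entry uniform over A months of 30.44 days before the stop; an EOS examination at the stop; 24-week risk 60%; constant hazard. Visits are at Days 28, 61, 91 and 182 with the Table 5-1 windows. The share reaching Month 6 is about (A − 182)/A with A in days: (243.5 − 182)/243.5 = 25%, (304.4 − 182)/304.4 = 40%, (365.3 − 182)/365.3 = 50%. Simulation, 40,000 runs per setting:

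| Accrual (months) | 8 | 10 | 12 |
|---|---|---|---|
| Sham recurrences outside the row (mean) | 4.1 | 3.3 | 2.7 |
| Share of observed recurrences outside | 64% | 47% | 37% |
| Mean of SAP row (true Month 6 risk 0.628) | 0.621 | 0.622 | 0.625 |
| RMSE, SAP row | 0.279 | 0.210 | 0.183 |
| Mean, half-at-risk life table | 0.605 | 0.613 | 0.617 |
| RMSE, half-at-risk life table | 0.164 | 0.154 | 0.147 |
| Mean if dropped recurrences are added to numerator and denominator | 0.816 | 0.756 | 0.725 |

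Estimates are conditional on at least one sham subject attending Month 6. If the hazard is four times higher after Day 84, the shares outside are 57/40/30%. At 30% risk they are 62/44/35% (constant) and 54/37/28% (rising).

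**Step 4: short accrual.** With 6 months (182.6 days) only about 4% of subjects reach Month 6, and 0.96^15 = 54% of runs have no sham row (0.96^8 = 72% with 8 subjects). With 4 months (121.8 days) nobody reaches Day 154, so there is never a row.

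**Step 5: shortcuts that fail.** Adding the dropped recurrences to both numerator and denominator overstates risk by 19/13/10 points (0.816, 0.756 and 0.725 minus 0.628). Dividing all observed recurrences by all randomized understates it: with follow-up at the stop uniform from week 1 to week 30, 36 or 48, a true 40% risk appears as 25% to 31%.

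**The case against.** **The restriction is open and permitted.** SAP 4.2.1 states it with its reason, and SAP 3.1 allows exceptions. A reader might infer a breach of ITT; the text does not support that. Its absence from 4.8 is housekeeping.

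**The events do not vanish.** A reader might infer that they survive only in listings. That is not so. SAP 4.2.2 tabulates both components by scheduled visit and does not repeat the Week 24 limit. In the illustration, 44% to 73% of the dropped recurrences were already present at an attended scheduled visit. SAP 4.3.1.3 read with 4.3.2 most naturally counts recurrences in all ITT subjects. Some events may also surface as ocular adverse events or rescue use. What remains missing is narrower: the component tables do not combine the criteria per subject or apply the attribution step, may not show EOS findings, and are not split by reaching Week 24.

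**No bias is shown.** A reader might infer that the row distorts the comparison in favour of one arm. The stop was for reasons other than safety or efficacy, and under a stop unrelated to outcome the row stays centred (0.62 against 0.63).

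**Scope.** The SAP Introduction says the endpoint list was deliberately reduced, and time to recurrence went with it. A supplementary estimate partly reverses that choice. It is a reasonable addition, not the repair of an error.

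**The remedy is weakest where the loss is greatest.** With very short accrual there is no 24-week estimate to give.

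**Unmasking.** Protocol 3.1 says all subjects were unmasked and sham subjects had an EOS visit, without giving the order. EOS findings may therefore be unmasked and need separate display.

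These objections limit the point to a minor one. They do not supply the split or an estimate that uses partial follow-up.

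**Conclusion.** The point holds as a minor one. Under SAP 4.2.1, composite, uveitis-attributed recurrences observed before an early stop leave the primary row. The sponsor's stop causes this in sham only; other early leaving can cause it in either arm. No planned table splits these recurrences by whether Week 24 was reached, and none gives a 24-week estimate from partial follow-up.

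If leaving is unrelated to outcome, the cost is precision. Under the Step 3 assumptions the RMSE of the sham row is 0.28 to 0.18, against 0.16 to 0.15 for a life table. The SAP is descriptive with no testing (4.1.1), so no error rate or decision rule is affected. The true size is unknown. For Yutiq subjects who leave early, the direction of any bias cannot be stated from the documents.

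The Week 52 denominator is unclear in the same way: SAP 4.3.1.1 refers back to the primary endpoint, while 4.3.2 says ITT on observed data.

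**What to change.** Keep the row for subjects who reached Week 24. Before database lock, add by arm:

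- **Counts:** the numbers randomized, reaching Week 24 and not reaching it, with recurrences observed after Day 7 in those not reaching it. Show EOS/ET findings separately and state whether they were assessed before or after unmasking. The numbers of subjects are largely available from SAP 4.4.1 and 6.2.1.
- **A supplementary 24-week estimate** in all randomized subjects, by Kaplan-Meier or life table on nominal visits, read at Month 6, with 95% CI and numbers at risk. If nobody in an arm attended Month 6, report it only to the last scheduled visit attended. Fix the EOS/ET convention and the CI method in advance.

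Do not simply add the dropped recurrences back. List the Week 24 denominator in SAP 4.8 and state the Week 52 denominator in 4.3.1.1 or 4.3.2.

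**Cost.** SAP wording and one extra table, with no new data. The estimate assumes that leaving is unrelated to outcome. Intervals stay wide: in the illustration the median 95% CI width is 0.62/0.59/0.57, against 0.80/0.72/0.67 for the existing row. The half-at-risk convention runs about 1 to 3 points low with constant hazard and 2 to 5 with rising hazard at 8 to 12 months' accrual, and about 5 and 9 points low at 6 months. Using scheduled visits only runs 0.3 to 2 points low but gains less precision (RMSE 0.23/0.19/0.17 with constant hazard), and runs 10 to 11 points low at 6 months.

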3 INVESTIGATIONAL PLAN

3.1 Overall Study Design

[figure not shown]
The protocol was originally planned to be a 52-week, prospective, randomized, masked (subject and outcome assessor), controlled, safety and efficacy study of intravitreal Yutiq 0.05 mg compared to sham injection with a primary efficacy and safety readout at 24 weeks.

The Sponsor has decided to stop enrollment for reasons other than safety or efficacy in early May 2022, following FDA advice received on January 24, 2022. The Sponsor is reevaluating the development program of Yutiq 0.05 mg. Subject enrollment has been stopped, and all subjects have been unmasked. Subjects who were randomized to the sham injection were discontinued from the study and underwent their EOS visit. Subjects who were randomized to sham injection may have been treated with standard of care medication, if necessary. Subjects who were randomized to Yutiq 0.05 mg will be followed on a modified protocol schedule through Month 12 (or ET) and evaluated for efficacy and safety.

As depicted in [Figure 3-1](#), subjects will receive either Yutiq 0.05 mg or a sham injection on Day 1 of the study. Subjects who were treated with Yutiq 0.05 mg will be assessed over the following 52 weeks on a modified protocol schedule according to the schedule presented in

Table 5–1. Subjects who were randomized to the sham injection were discontinued from the study and underwent their EOS visit.

Figure 3-1: Study Design Schema, Study EYP-2102-001

Note: The sponsor decided to stop enrollment for reasons other than safety or efficacy in early May 2022, following FDA advice received on January 24, 2022. The Sponsor is reevaluating the development program of Yutiq 0.05 mg. Subject enrollment in the study has been stopped. All subjects who were currently enrolled have been unmasked. Subjects who were to receive Yutiq 0.05 mg will be followed on a modified protocol schedule through Month 12 (or ET).

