4.3. Secondary Endpoints Analysis

4.3.1. Definition of Secondary Endpoints

The secondary efficacy endpoints will include the following endpoints:

4.3.1.1. Proportion of subjects who have a recurrence of uveitis in the study eye within 52 weeks

The recurrence of uveitis will be assessed the same as the primary efficacy endpoint within 52 weeks.

4.3.1.2. Mean change from baseline in BCVA letter score in the study eye at 24 and 52 weeks

The change from baseline in BCVA as measured by ETDRS letter at each visit will be calculated.

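### The Week 24 recurrence display counts Yutiq subjects randomised up to early May 2022 but sham subjects only if randomised about 20 to 24 weeks earlier, so the later Yutiq subjects have no concurrent sham counterpart in it

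*SAP*

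**What the plan says.** SAP 4.2.1 drops the protocol's rule that counted non-completers and users of prohibited medication as recurrences: "Consider the fact that the study was terminated early, no imputation will be implemented". It then says who is summarised: "Summary of the primary efficacy endpoint will be based only on the observed data from the subjects who reached Week 24".

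SAP 4.1.3 takes the Week 24 endpoints from the nominal Month 6 visit and the Week 52 endpoints from Month 12, without re-mapping visits. SAP 4.2.2 gives a Clopper-Pearson interval for the recurrence rate. SAP 4.8 replaces the planned test: "Instead, the number and proportion of subjects who experience the uveitis recurrence will be summarized by treatment group".

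The two arms were followed differently after the stop:

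- SAP 1.2: "The Sponsor decided to stop enrollment in early May 2022 for reasons other than safety or efficacy, following FDA advice received on January 24, 2022".
- Protocol Synopsis, Follow-up Visits: "In early May 2022, those subjects who had been treated with sham injection were discontinued from the study".
- Protocol 3.1, on the other arm: "Subjects who were randomized to Yutiq 0.05 mg will be followed on a modified protocol schedule through Month 12 (or ET) and evaluated for efficacy".
- Protocol 3.1 also records: "Subject enrollment has been stopped, and all subjects have been unmasked".

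For the Week 52 proportion, SAP 4.3.1.1 carries the same approach forward: "The recurrence of uveitis will be assessed the same as the primary efficacy endpoint within 52 weeks".

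**The concern.** Randomisation was 1:1 for as long as enrolment was open, so at any calendar time each arm has counterparts in the other. The Week 24 summary does not keep that balance. Its entry condition is having reached a visit, and the stop made that visit unreachable for recently randomised sham subjects but not for recently randomised Yutiq subjects. Nothing in SAP 4.2.1, 4.2.2 or 4.8 restricts the Yutiq row to match or flags the difference.

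The late Yutiq subjects differ from the rest of the display in more than calendar time. Their Month 6 examination took place after the stop, when assignments had been disclosed. Recurrence rests partly on clinician-graded vitreous haze and on a judgement about its cause, so knowing that an eye holds a steroid insert could affect what is recorded. Any difference between early and late subjects, whatever its source, enters the Yutiq percentage only and would look like a difference between arms.

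**Working it through.** There is no figure in the plan to reproduce: neither document states a cut-off for sham entry. The planned size is about 60 subjects, 30 per arm.

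**Inputs**

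- Sham discontinuation: early May 2022 (Protocol Synopsis), taken here as 1 to 10 May.
- Last possible randomisation in either arm: early May 2022 (SAP 1.2).
- Month 6 visit: Day 168 if 24 weeks. The window is ±28 days (Protocol Table 5-1), so the earliest in-window visit is Day 140.
- Not given: first enrolment date, numbers randomised by arm or month, sham end-of-study visit dates, and a separate date for unmasking, which I take to be about the time of the stop.

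**Step 1: latest randomisation date for a sham subject in the Week 24 row** = stop date − day of the Month 6 visit.

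| Stop date | −168 days | −140 days |
|---|---|---|
| 1 May 2022 | 14 Nov 2021 | 12 Dec 2021 |
| 10 May 2022 | 23 Nov 2021 | 21 Dec 2021 |

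If Month 6 is read as 182 days, the nominal cut-off becomes 31 October to 9 November 2021, and 28 November to 7 December at the early window edge. If sham end-of-study visits ran to 31 May 2022 and counted as Month 6, the cut-off moves to 14 December 2021 (168 days) or 11 January 2022 (140 days).

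**Step 2: Yutiq subjects.** No such limit applies. A subject randomised in early May 2022 reaches Month 6 in the autumn of 2022 and is counted. Anyone randomised less than 140 days before the stop can have an in-window Month 6 visit only after it. Between 140 and 168 days, this depends on when in the window the visit fell.

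**Step 3: share of the Yutiq row without a concurrent sham subject** = (140 or 168) / days of enrolment. This assumes uniform enrolment to 5 May 2022 and equal retention of early and late Yutiq subjects.

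| Assumed first enrolment | Days to 5 May 2022 | 140 days | 168 days |
|---|---|---|---|
| 1 Jan 2021 | 489 | 29% | 34% |
| 1 Jun 2021 | 338 | 41% | 50% |
| 1 Sep 2021 | 246 | 57% | 68% |
| 1 Nov 2021 | 185 | 76% | 91% |
| 1 Dec 2021 | 155 | 90% | 100% |

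**Step 4: scale of the effect.** Shift in the Yutiq rate = share × (late rate − early rate). The documents report no such difference, so this gives a scale, not an estimate. For every 10 points of difference, the rate moves by 0.29 × 10 = 2.9 points to 0.68 × 10 = 6.8 points across the January to September 2021 starts.

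**Step 5: Week 52.** With Month 12 at Day 364, a sham subject must have been dosed by 2 to 11 May 2021. At the early window edge (Day 336) the date is 30 May to 8 June 2021.

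**The case against.** The strongest reply is that the SAP compares nothing. SAP section 2 has no hypotheses, SAP 4.1.1 makes every summary descriptive, and 4.8 drops the test for lack of sample size. Each arm gets its own interval, with no difference and no p-value. The sham discontinuation is stated openly, and numbers remaining by visit, duration of participation and by-subject listings would let a careful reader see the asymmetry. This stands as far as error rates go: no type I error is at stake. It does not settle how the result is read. Two percentages for the primary endpoint, laid out by randomised arm with exact intervals, will be compared, and SAP 4.8 does not warn that the arms cover different enrolment periods.

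The cut-off is also not exact, because sham end-of-study visits are undated. That moves the date by some weeks; it does not remove the mechanism. The protocol (11.3.3) would map early-termination visits to the next scheduled visit, which could have turned some sham end-of-study visits into Month 6, but SAP 4.1.3 allows no re-mapping.

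A reader might infer more than the documents support:

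- *That the control is not concurrent.* Every sham subject in the row was randomised 1:1 alongside the earlier Yutiq subjects. Only later Yutiq subjects lack a counterpart.
- *That most of the Yutiq row is affected.* This depends entirely on an enrolment start that is not given. At the latest assumed starts the sham row is nearly empty, so there is little side by side to misread.
- *That the administrative letters of 3 January and 1 March 2022 put the two arms under different examination instructions.* What matters is the examination date. A sham subject dosed after about 14 September 2021 (1 March 2022 − 168 days) had the nominal Month 6 visit after both letters. The letters are known only as clarifications in the summary of changes.

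**Conclusion.** The point holds as a matter of presentation. Yutiq subjects randomised in the last 20 to 24 weeks before the stop enter the Week 24 row with no concurrently randomised sham subject, and with a Month 6 examination after the stop and unmasking.

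The dates rest on a stop between 1 and 10 May 2022 and the ±28-day window. The share rests on uniform enrolment and an assumed start, and the documents fix neither it nor the direction of any resulting distortion. At Week 52 the problem is plainer: the sham column would be empty or hold only subjects dosed by about May to early June 2021.

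No test is invalidated. This is an inexpensive improvement to a display that would otherwise invite a comparison that randomisation only partly supports.

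**What to change.** In SAP 4.2.1 and 4.2.2, state the exact sham discontinuation date and add a concurrent row. In both arms it holds only subjects whose nominal Month 6 visit took place on or before that date. Use this row for the side-by-side display. Defining it by visit date respects the ±28-day window. A flat 24-week cut on randomisation date would not: it would exclude a subject with a valid visit at Day 150 and admit one whose visit fell after the stop.

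Keep all Yutiq subjects who reached Week 24 as a separate single-arm row, labelled as partly without concurrent control. Apply the same rule to BCVA change at Week 24. Present Week 52 recurrence and BCVA for Yutiq only, unless a sham subject had a Month 12 visit by that date. List the change in SAP 4.8.

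The cost is SAP wording and one extra row from dates already held. The concurrent Yutiq row will be smaller and its exact interval wider, but no Yutiq data are lost from the report.
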